9 ADVERSE EVENTS

9.1 Definition of Adverse Event

An adverse event (AE) is defined as any untoward medical event in a patient regardless of its causal relationship to study treatment. An AE can be any unfavorable and unintended sign (including any clinically significant medical test abnormality), symptom, or disease temporally associated with the use of study drug, whether or not it is considered related to study drug administration. Included in this definition is any newly occurring event or previous condition that has increased in severity or frequency since the administration of study drug.

A medical test abnormality (e.g., laboratory test value, vital sign recording, ECG finding, physical examination finding) will be considered clinically significant and consequently recorded as an AE only if it meets one of the following criteria:

- Induces clinical signs or symptoms
- Requires active intervention
- Requires interruption or discontinuation of study medication

9.2 Definition of Serious Adverse Event

A serious adverse event (SAE) is any AE occurring at any dose and regardless of causality that:

- Results in death
- Is life-threatening
- Requires hospitalization or prolongation of existing hospitalization
- Results in persistent or significant incapacity or substantial disruption of the ability to conduct normal life function
- Is a congenital anomaly or birth defect in an offspring of a patient receiving study drug
- Is an important medical event

The term "life-threatening" refers to an event in which the patient was at immediate risk of death at the time of the event. It does not refer to an event that hypothetically might have caused death if it were more severe.

Important medical events are those that may not need any of the criteria defined above; however, they may be considered serious when, based upon appropriate medical judgment, they may jeopardize the patient and may require medical or surgical intervention to prevent one of the other outcomes listed in the SAE definition.

Pregnancy is not considered an AE; however, information will be collected for any pregnancies that occur during study drug administration or the thirty days thereafter. Certain pregnancy outcomes will require submission as an SAE.

9.3 Eliciting Adverse Event Information

At every AE/SAE assessment, the patient must be asked a standard, non-directed question, such as, "how have you been feeling since your last visit?" to elicit any medically related changes in their well-being. In addition, the hospital chart and other documents relevant to patient safety must be reviewed when the patient is in the hospital.

9.4 Recording Adverse Events

Recording of AEs must begin after randomization. All conditions present before randomization, including untoward medical events during Screening, should be documented as medical history. Documentation shall continue until the patient dies, the patient withdraws consent, or the patient's participation in the study ends. Information to be collected includes:

- Type of event
- Date of onset
- Date of resolution
- Investigator-specified relationship to study drug and assessment of severity
- Seriousness
- Any action taken

While an AE is ongoing, changes in the severity (e.g., worsening and improving) should be noted in the source documents, but when documenting the AE, only the total duration and the greatest severity should be recorded in the case report form. AEs characterized as intermittent require documentation of onset and duration.

All AEs reported or observed during the study must be followed to resolution. Or, if not fully resolved, until the condition has stabilized, the patient dies, withdraws consent, the site is closed, or CalciMedica ends the trial, whichever is first.

AEs resulting from concurrent illnesses, reactions to concurrent medications, or progression of disease states must also be reported. Pre-existing conditions (present before the start of the AE collection period) are considered concurrent medical conditions and should NOT be recorded as AEs. However, if the patient experiences a worsening or complication of such a concurrent condition, the worsening or complication should be recorded as an AE. Investigators should ensure that the AE term recorded captures the change in condition (e.g., "worsening of...").

Each AE should be recorded to represent a single diagnosis. Accompanying signs (including abnormal laboratory test values or ECG findings) or symptoms should NOT be recorded as additional AEs. If a diagnosis is unknown, sign(s) or symptom(s) should be recorded as an AE(s).

Elective procedures (surgeries or therapies) performed to manage/treat conditions that existed prior to the patient enrolling in the trial should not be recorded as AEs but should be documented in the patient's source documents. If a planned procedure is performed early (e.g., as an emergency) because the pre-existing condition worsens, the worsening condition should be captured as an AE.

9.5 Assessment of Relationship to Study Drug

The Investigator must use the following classification and criteria to characterize the relationship or association of study drug in causing or contributing to the AE:

- **Unrelated**: This relationship suggests that there is no association between study drug and the reported event
- Unlikely: This relationship suggests that there is an unlikely association between study drug and the reported event
- **Possible**: This relationship suggests that treatment with study drug caused or contributed to the AE. That is, the event follows a reasonable temporal sequence from the time of study drug administration, and/or follows a known response pattern to the study drug, but could have been produced by other factors
- **Probable**: This relationship suggests that a reasonable temporal sequence of the event with study drug administration exists and, based upon the known pharmacological action of the drug, known or previously reported adverse reactions to the drug or class of drugs, or judgment based on the Investigator's clinical experience, the association of the event with study drug administration seems likely
- **Definite**: This relationship suggests a definite causal relationship exists between study drug administration and the AE, and other conditions (concurrent illness, progression/expression of disease state, or concurrent medication reaction) do not appear to explain the event

9.6 Assessment of Severity

The Investigator must use the following criteria to rate the intensity of the AE:

- **Mild**: Symptoms causing no or minimal interference with usual social and functional activities
- **Moderate**: Symptoms causing greater than minimal interference with usual social and functional activities
- Severe: Symptoms causing inability to perform usual social and functional activities

9.7 Reporting of Serious Adverse Events

The Investigator is responsible for reporting to CalciMedica or designee within 24 hours from the time when site personnel learn about the event, all SAEs that are observed or reported by the patient during the study (from randomization until the patient dies, the patient withdraws consent, or the patient's participation in the study ends) regardless of the relationship to study drug or clinical significance. Any additional information that becomes available later should be submitted within 1 working day of receipt. All SAEs reported or observed during the study must be followed to resolution or until the Investigator deems the event to be chronic or the patient to be stable. CalciMedica or its designee may contact the Investigator to obtain additional information on any SAE that has not resolved at the time the patient completes the study. SAEs ongoing at database lock will be noted as such. The PIs are also responsible for informing their IRB/EC of any SAEs at their site. SAE correspondence with IRBs/ECs must be submitted to CalciMedica or its designee for filing.

A study manual will contain the details needed to report SAEs. If any questions on SAEs, contact information is as follows:

SAE reporting email address: [contact]

• **SAE [contact] (toll free)

• **SAE [contact]

CalciMedica will notify the FDA in a written safety report of any suspected adverse reaction or adverse reaction associated with the use of Auxora that is serious and unexpected.

- Suspected adverse reaction means any AE for which there is a reasonable possibility that the drug caused the AE. For the purposes of IND safety reporting, 'reasonable possibility' means CalciMedica determines that there is evidence to suggest a causal relationship between the drug and the AE (definite, probable, possible) regardless of the investigator's causality assessment
- Adverse reaction means any AE caused by a drug. Adverse reactions are a subset of all
 suspected adverse reactions where there is reason to conclude that the drug caused the
 event
- Serious, as defined in Section 9.2
- Unexpected AE or suspected adverse reaction refers to an event or reaction that is not listed in the investigator's brochure or is not listed at the specificity or severity that has been observed

CalciMedica or its designee will notify the FDA of any unexpected serious suspected adverse reactions associated with the use of Auxora that are fatal or life threatening as soon as possible but no later than seven calendar days after the initial receipt of the information. Initial notification will be followed by a written report within fifteen calendar days.

CalciMedica or its designee will notify the FDA of any unexpected serious suspected adverse reactions associated with the use of Auxora that are not fatal or life threatening fifteen calendar days.

CalciMedica or its designee will provide copies of any reports to regulatory agencies regarding unexpected serious suspected adverse reactions associated with the use of Auxora to the Investigators for review and submission to the IRB/EC.

In addition, if any of the events below, which are commonly observed **and thus** 'anticipated' in this patient population, are reported as a SAE, they will not be reported to the regulatory authority as individual expedited reports except in unusual circumstances or if required by local regulations:

- Hypoxemia and acute respiratory distress syndrome
- Oliguria and acute kidney injury
- Hypotension and shock
- Bacteremia
- Pneumonia
- Obtundation
- Splanchnic venous thrombosis
- Abdominal compartment syndrome
- Gastroparesis and ileus
- Local complications of the pancreas and peripancreatic tissue
- Percutaneous insertion of abdominal drains
- Endoscopic necrosectomy
- ERCP
- Abdominal surgery including but not limited to cholecystectomy, pancreatic necrosectomy, and placement of pancreatic drains

9.8 Suspected Pregnancy in a Woman of Childbearing Potential

A female patient of childbearing potential is a female who is not surgically sterile (no history of a bilateral salpingo-oophorectomy) and is not postmenopausal for at least 1 year.

A female patient of childbearing potential who receives study drug and is sexually active with a male partner, and a male patient who receives study drug and is sexually active with a female of childbearing potential, must be willing to use two highly effective methods of contraception (e.g., barrier methods, spermicidals, intrauterine devices, and/or hormonal contraception) for

180 days after last dose of study drug. No contraception is required if a female patient or partner has undergone a bilateral salpingo-oophorectomy.

Two of the following methods of birth control must be practiced unless a sexually active female patient or partner of childbearing potential has undergone a bilateral salpingo-oophorectomy:

- Male partner has a vasectomy for at least six months duration
- Use of an intrauterine device
- Use of hormonal contraceptives (oral, parenteral, vaginal or transdermal)
- Double barrier contraception with the male partner using a condom and the female using a contraceptive sponge, spermicidal jelly or cream or diaphragm plus spermicidal jelly or cream

The Investigator should be immediately informed if a female patient or partner of childbearing potential suspects she is pregnant up to 180 days after last dose of study drug. If the female patient is receiving study drug when discovered to be pregnant, the study drug should be immediately discontinued. If a pregnancy is confirmed, the Investigator must immediately report a pregnancy and record the event using a Pregnancy Report Form. Pregnancy is not considered an AE but the Investigator must follow a pregnant patient or partner. The Investigator must report follow-up information regarding the course of the pregnancy, including perinatal or neonatal outcome. Infants resulting from such pregnancies should be assessed for normality at birth and should be followed for 6 months to assess for development milestones. CalciMedica or its designee may contact the Investigator to request additional information throughout the course of the pregnancy.

The following pregnancy outcomes must be considered SAEs and will require additional reporting in the eCRF and on an SAE form:

- Congenital anomaly/birth defect
- Stillbirth
- Spontaneous miscarriage

10 STATISTICAL METHODS

10.1 General Considerations

Data summaries and listings will be generated using SAS version 9.3 or a more recent version (SAS Institute Inc., Cary, NC, USA).

The statistical analysis plan (SAP) and/or the clinical study report will provide additional details of the analysis, which may include details of missing and, if applicable, unused data, as well as additional sensitivity analyses of the primary and secondary variables. The clinical study report will describe deviations from the SAP, if any.

The statistical analysis approach will be descriptive, exploratory and inferential to determine the relationship between dose response and endpoints in identifying the optimal dose and primary endpoint(s); also, in identifying the priority order of sequential testing for secondary endpoints.

10.2 Sample Size

A sample size of 216 patients will be randomized into four groups on a 1:1:1:1 basis, resulting in 54 patients randomized into each group. This sample size will provide 86% power for testing the difference in two populations having a median length of time of 72 and 144 hours, respectively, to tolerating solid food based on a log-rank test. This sample size will provide 80% power with a two-sided alpha of 0.05 (using the chi-squared test) to detect a 45% response rate for tolerating solid food in a Auxora dose group versus a 20% response rate in the Placebo group in the 72 hours after completion of the first study drug infusion.

10.3 Study Assessments

Efficacy assessments will include:

- Enhanced Recovery Strategy for Tolerance of Solid Food
- Modified Gastrointestinal Cardinal Symptom Index Score
- CECT of the Pancreas
- PNRS score
- Organ Failure scores
- Vital sign measurements
- Laboratory measurements
- Concomitant medications

Safety assessments will include:

- Vital signs measurements
- Laboratory measurements
- Concomitant medications
- TEAEs and SAEs

PK assessments and analyses will include:

- Adding the plasma concentration data to the current population PK model to refine the model and covariate analysis
- Using the revised population PK model to determine if AP disease severity alters PK properties of CM4620
- Determining whether a relationship exists between plasma trough levels of CM4620 and patient response to Auxora (i.e., an exposure-response relationship)

10.4 Analysis Sets

10.4.1 Efficacy and Safety

The efficacy analyses will be performed on the Modified Intent-to-treat Population (MITT) consisting of all randomized patients who receive any amount of study drug.

As the sensitive analysis, the primary efficacy analyses will also be performed on the Per-Protocol Population (PP) consisting of all randomized patients who complete the study and have no major protocol violations.

The safety analyses will be performed on MITT data set.

10.4.2 Pharmacokinetics

The PK population will consist of all randomized patients who receive any amount of active study drug and who have at least one post baseline PK sample analyzed.

10.5 Disposition

The number and percentage (n, %) of patients enrolled, screen failed, treated, completed study, and discontinued (with reason) will be summarized. Sample size for each analysis population will be identified for each treatment group. All screened patients will be included in the disposition analysis.

10.6 Analysis of Demographic and Baseline Data

Patient demographic and baseline characteristics will be summarized by mean, standard deviation, median, minimum, and maximum for continuous variables; and by counts and percentages for categorical variables. Summaries will be provided separately for each treatment group.

10.7 Efficacy Analysis

The efficacy endpoints are the following:

Primary endpoint

Time to solid food tolerance

Secondary endpoints

- Solid food tolerance at 48 hours, 72 hours, and 96 hours after the SFISD and at discharge
- Time to medically indicated discharge
- Length of stay in the hospital
- Length of stay in the ICU for patients admitted to the ICU
- Re-hospitalization for AP by Day 30
- Change in severity of AP by CTSI score from screening to Day 30
- Development of pancreatic necrosis ≥30% and >50%
- The persistence of SIRS ≥48 hours after the SFISD
- Incidence, severity, and duration of organ failure
- Mortality by Day 30
- Change in pain score and opioid use

Exploratory endpoints

- Development of infected pancreatic necrosis
- Development of sepsis
- Hospital procedures for the management of pancreatic necrosis
- Change in GCSI-DD score
- Change in albumin
- Change in ANC/ALC ratio and IL-6 levels
- Change in urine NGAL

Time to solid food tolerance is the number of hours from the date and time of the SFISD for the patient to the first date and time the patient receives a solid meal that is tolerated, which is defined as eating \geq 50% of a low fat, \geq 500-calorie solid meal without an increase in abdominal pain or vomiting in the two hours after completing the meal.

Time to solid food tolerance for patients who could not tolerate solid food during the study will be censored on the latest date and time of food tolerance assessment.

Time-to-event endpoints will be summarized using Kaplan-Meier analyses. The medians and quartiles of time-to-events will be summarized. Time to solid food tolerance will be compared between each treatment groups and the placebo group using the stratified log-rank test as the primary analysis. The tests will be at an alpha level of 0.05 without multiplicity adjustment. The stratification variables will include gender (male vs. female) and disease severity status (higher

risk for organ failure defined by the presence of both a HCT \geq 44% for men, or \geq 40% for women, and a PaO₂/FiO₂ \leq 360 before randomization (Figure 4).

In addition, the hazard ratio (HR) and the 95% CI will be estimated using a Cox proportional-hazard model with treatment group as the independent variable and stratified by the same randomization stratification factors as used for the log-rank test.

10.8 Safety Analysis

Safety will be assessed by subject reported and Investigator observed AEs along with clinical laboratory tests (hematology and chemistries), and vital signs. Safety variables will be tabulated by treatment groups and presented for all treatment patients. Exposure to study treatments, reasons for discontinuation, deaths and causes of deaths will be tabulated. TEAEs are defined as events that first occurred or worsened after the first dose of study drug. TEAEs will be mapped to the appropriate SOC and PT according to the Medical Dictionary for Regulatory Activities (MedDRA).

Summaries will be provided for all AEs, AEs considered related to study treatment, SAEs, and related SAEs as follows:

- By maximum severity
- Incidence by SOC (by severity grade and overall)
- Incidence by PT (by severity grade and overall)

The percentage of 30 day all-cause mortality will be calculated based on each subject's date of death relative to first dose of study treatment and tabulated by treatment groups.

Laboratory test results will be used in the summary. The lower and upper reference range values for blood tests from the laboratories will be used to grade the lab results to low, normal and high. Shift tables will display (1) shift from baseline grade to the worst grade, and (2) shift from baseline grade to the last grade. Vital signs will be summarized by visit using proportion of patients with each vital sign being too high or too low according to conventionally accepted vital sign normal ranges.

Concomitant medication will be coded by the WHO Drug Dictionary and summarized by Therapeutic subgroup and PTs, using counts and percentages. Concomitant medications are the medications taken with a start date on or after the start of the administration of study treatment, or those with a start date before the start of the administration of study treatment and a stop date on or after the start of the administration of study treatment.

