8.12.4 Vital Signs

The patient's temperature, heart rate (beats per minute), systolic and diastolic blood pressures and respiratory rate (breaths per minute) closest to the time of assessment should be recorded. If intra-abdominal pressures are being monitored, the pressure closest to the time of assessment should be recorded.

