Appendix 1. Definition of Organ Failure and Sepsis

The definition of organ failure encompasses three organ systems, respiratory system, renal system and cardiovascular system.

For the respiratory system, organ failure will be defined as:

- PaO₂/FiO₂ ≤300 determined by arterial blood gas or imputed using pulse oximetry, or
- The use of high flow nasal cannula, non-invasive or invasive mechanical ventilation

For the renal system, in patients without known chronic kidney disease (baseline eGFR ≥60 mL/min/1.73 m²), organ failure will be defined as:

- An increase in serum creatinine ≥300% if the baseline creatinine is known from prior to the hospitalization for AP, or
- A serum creatinine ≥ 1.9 mg/dL, or
- The initiation of renal replacement therapy

For patients with pre-existing chronic kidney disease (baseline GFR <60 mL/min/1.73 m²), organ failure will be defined as:

- An increase in serum creatinine ≥300% if the baseline creatinine is known from prior to the hospitalization for AP, or
- An increase of serum creatinine to a level >4.0 mg/dl, or
- The initiation of renal replacement therapy

For the cardiovascular system, organ failure will be defined as:

- A systolic blood pressure <90 mmHg that is not fluid responsive, or
- The use of either vasopressor or inotropic support

Sepsis is the life-threatening organ dysfunction caused by a dysregulated host response to infection. For this study, organ dysfunction in the setting of infection will be defined by the presence of one of the following criteria:

- PaO₂/FiO₂ ≤300 determined by arterial blood gas or imputed using pulse oximetry
- The use of noninvasive or invasive mechanical ventilation
- Platelet count <100 x10³/uL
- Total bilirubin ≥2.0 mg/dL
- The use of vasopressor or inotropic support
- Serum creatinine ≥1.9 mg/dL in patients without pre-existing chronic kidney disease

- Serum creatinine >4.0 mg/dL in patients with pre-existing chronic kidney disease
- An increase in serum creatinine ≥300% if the baseline creatinine is known from prior to the hospitalization for acute pancreatitis
- The initiation of renal replacement therapy

Modified Marshall Scoring System: Organ Dysfunction in Acute Pancreatitis

		0 (None)	1 (None)	2 (Mild)	3 (Moderate)	4 (Severe)
Respiratory	PaO ₂ /FiO ₂	>400	301-400	201-300	101-200	≤100
Renal	Serum Cr mg/dL	<1.4	1.4-1.8	1.9-3.6	3.7-4.9	>4.9

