8.10.2 Vital Signs

Vital signs will include temperature, systolic and diastolic blood pressure, respiratory rate (breaths per minute), heart rate (beats per minute) and QTc (milliseconds). Vital signs will be examined at each scheduled visit and time point. Clinically significant, treatment-emergent findings will be reported as AEs. In addition, vital signs results will be flagged as potentially clinically significant (PCS) if they meet the criteria which are defined below:

- Pulse rate >130 bpm
- Pulse rate <45 bpm
- Diastolic blood pressure >100 mmHg
- Systolic blood pressure >155 mmHg
- Systolic blood pressure <80 mmHg
- Respiration rate >25 breaths/min
- Body temperature ≥39 °C
- OTc >500 milliseconds

The number and percent of patients meeting each PCS criterion at each scheduled visit and time point will be summarized by the actual treatment and then by the overall treatment.

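### The SAP's vital-sign table has no low limit for temperature, respiration or diastolic pressure, so it does not deliver the two-sided summary promised in Protocol 10.8, and SAP section 13 does not record the departure

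*Protocol*

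**What the plan says.** Protocol 10.8 (Safety Analysis) commits to a by-visit summary of the "proportion of patients with each vital sign being too high or too low according to conventionally accepted vital sign normal ranges". Protocol 8.12.4 names the vital signs collected: temperature, heart rate, systolic and diastolic blood pressure, and respiratory rate. Clinically significant changes in vital signs are a named safety endpoint in both documents (Protocol 2.4, SAP 5.2).

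SAP 8.10.2 (Vital Signs) defines a PCS list and plans the number and percentage of patients meeting each PCS criterion at each scheduled visit, by treatment. The low-side entries are "Pulse rate <45 bpm" and "Systolic blood pressure <80 mmHg". Temperature appears only as "Body temperature ≥39 °C", diastolic pressure only as "Diastolic blood pressure >100 mmHg", and respiration only as a high limit of more than 25 breaths per minute. QTc above 500 ms is also listed.

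Elsewhere the documents use other figures for the same signs. The SIRS criteria (Protocol 8.12.13, SAP 8.7.7) use temperature below 36 °C or above 38 °C, heart rate above 90 and respiratory rate above 20. For cardiovascular failure, Appendix 1 of the protocol uses "A systolic blood pressure <90 mmHg that is not fluid responsive".

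SAP section 13, which lists changes from the protocol-planned analysis, has one entry: length of stay in the ICU.

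**The concern.** The protocol describes a table with two sides for each sign. The SAP, which is what will be programmed, specifies a table with one side for three of the five signs. Followed as written, it will contain no row in which a low temperature, a low respiratory rate or a low diastolic pressure can be counted. A systolic reading from 80 up to just below 90 mmHg will not be counted either.

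This is a dose-ranging trial, and SAP 8.6.1 (Step 3) says the final dose choice will weigh safety endpoints as well as efficacy. A one-sided table cannot show a dose-related rise in the share of patients with low values for those three signs. Because SAP section 13 is silent, a reader of the final report would not learn that the planned summary had been narrowed.

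**Working it through.** There is no stated sample size, power or error rate behind this point, so there is no plan figure to reproduce. The check sets the texts side by side.

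**Step 1: limits per sign.** The signs come from Protocol 8.12.4, the limits from SAP 8.10.2, and the last column from the SIRS criteria and Appendix 1.

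| Sign | High limit | Low limit | Figure used elsewhere in the documents |
|---|---|---|---|
| Temperature | ≥39 °C | none | <36 °C or >38 °C (SIRS) |
| Heart rate | >130 | <45 | >90 (SIRS) |
| Respiratory rate | >25 | none | >20 (SIRS) |
| Systolic pressure | >155 | <80 | <90 and not fluid responsive (Appendix 1) |
| Diastolic pressure | >100 | none | none |

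High limit present: 5 of 5. Low limit present: 2 of 5. Low limit absent: 5 − 2 = 3 of 5.

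For systolic pressure, the low flag sits 90 − 80 = 10 mmHg below the pressure figure in Appendix 1. In this table a patient at 35.5 °C, or one with a systolic pressure of 85 mmHg, cannot be counted. On the high side, the limits for temperature, heart rate and respiration are all wider than the SIRS figures, so moderately raised values are not flagged either.

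**Step 2: does another planned output supply the missing proportion?**

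- *Adverse events.* SAP 8.10.2 sends clinically significant findings to the AE tables. Under Protocol 9.1 an abnormal reading is an AE only if it induces signs or symptoms, needs active intervention, or leads to interruption or discontinuation of study drug. Protocol 9.4 adds that signs accompanying a recorded diagnosis are not entered as separate AEs.
- *SIRS at 48 hours (SAP 8.7.7).* Temperature below 36 °C contributes, but only at one time point, only as one of at least two criteria, and without separating low from high.
- *Organ failure (SAP 8.7.8).* New-onset persistent cardiovascular failure needs a modified Marshall score of at least 2 lasting at least 48 hours. Severe cardiovascular failure needs at least 48 hours of vasopressor or inotropic support. A transient low reading meets neither.
- *Generic descriptive statistics (SAP 8.1.3 and 8.10).* A mean and a minimum per arm may reasonably be expected. A minimum is one patient's extreme value, not a proportion of patients.

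None of the four gives a proportion of patients, per sign and per visit, with a low value.

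**Step 3: is the change declared?** SAP section 13 lists only the ICU item, so it is not.

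A side observation is that QTc is in the SAP list but is not among the vital signs in Protocol 8.12.4, and the Schedule of Events has no ECG row. That is consistent with a PCS list that was not matched to this protocol.

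**The case against.** The strongest reply has four parts.

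*Low values are not lost to the trial.* They can reach the AE tables, the SIRS endpoint, the organ failure analysis and the generic summaries. This stands, and it limits the claim. A reader might infer that most hypotension and all hypothermia go uncounted, but the documents do not support that. The statement about hypothermia is true only of the PCS table. The statement about hypotension needs a systolic distribution, and the documents give none. Under assumed normal distributions with mean 105 to 130 and SD 12 to 25 mmHg, the share of readings below 90 that lie between 80 and 90, [F(90) − F(80)] / F(90), runs from 42% to 96%. Whether it is a majority cannot be settled from the documents.

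*Appendix 1 is not a plain limit of 90 mmHg.* This also stands. The criterion requires pressure that is not fluid responsive, and a fluid-responsive value below 90 scores only 1 on the modified Marshall scale, in the column labelled as no dysfunction. A row for any reading below 90 is therefore a tabulation cut-off, not the organ failure definition. Likewise, one temperature criterion alone is not SIRS.

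*The SAP may supply detail.* Protocol 10.1 says so, and Protocol 10.8 does not state its normal ranges, so the exact cut-offs are a matter of judgement. That is fair for the values chosen. It does not cover dropping the low side for three signs, which contradicts a stated rule.

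*The stakes are modest.* Vital signs are single readings nearest each scheduled visit, with none scheduled at the first infusion. The table is descriptive and drives no test. This is correct and bears on priority.

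A reader might also argue that, because Protocol 9.7 treats hypotension and shock as anticipated events, this table is the only place an excess could be seen. That does not follow. Section 9.7 limits individual expedited reports to regulators. It does not remove these events from AE recording, SAE reporting to the sponsor, by-arm AE and SAE tables, or monitoring by the IDMC.

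**Conclusion.** The mismatch is real and can be verified from the text alone. SAP 8.10.2 does not deliver the two-sided by-visit summary of Protocol 10.8 for three of five collected signs. For a fourth, systolic pressure, the low flag starts only below 80 mmHg. The departure is not recorded in SAP section 13. Other outputs capture low values in part and do not replace the promised proportion per sign.

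The finding rests on no distributional assumption. It concerns the completeness of one descriptive table for a named safety endpoint. It does not affect the primary analysis, and it does not show that harm would go undetected across the trial as a whole. It is worth correcting because the commitment is explicit and the correction is cheap.

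**What to change.** Keep every existing PCS row in SAP 8.10.2 and add by-visit, by-arm rows for:

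- temperature <36 °C and temperature >38 °C, the figures the documents already use for SIRS;
- systolic pressure <90 mmHg, labelled as a tabulation cut-off, with a note that Appendix 1 adds the condition of not being fluid responsive;
- low diastolic pressure and low respiratory rate, each against a normal range that the SAP states.

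List any remaining difference from Protocol 10.8 in SAP section 13 with its rationale.

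These are reporting limits and change no patient care. The data are already collected, so the cost is a few more rows in one safety table. The downside is more flagged readings to review.
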